## 9 Trial treatments

### 9.1 Randomization and blinding

Subjects are enrolled and randomized consecutively as they are found to be eligible for inclusion in the trial. Randomization is performed no later than 12h before surgery. If a subject discontinues participation, the subject's trial-specific code will not be reused, and the subject will not be allowed to re-enter the trial.

Randomization will be performed online from within an electronic randomization system, after a multidisciplinary tumor board meeting, once all eligibility criteria have been verified and no exclusion criteria have been fulfilled. Randomization will be stratified by country and level of anastomosis (chest/neck). The electronic randomization module is accessed from each participating site. Treatment

Trial ID: ISRCTN16853684  
Version No: 1.0  
Date: January 27th 2026

allocation will be open-label, among the two intervention arms at a 1:1 ratio of paravertebral block and opioid PCA (intervention) or standard EDA treatment (control).

All randomized trial subjects will be recorded on the Participant Identification Code List, which includes the participant's name and personal identification number, date of informed consent and randomization date. It is the responsibility of the Investigator to keep the list updated throughout the trial and store it in a secure location to prevent unauthorized access.

No blinding will be used during treatment. Statisticians will be blinded at time of analysis after data-lock.

## 9.2 Preoperative analgesics (all)

Local routines regarding pain management are followed. We recommend that all patients will receive paracetamol (acetaminophen) 1000 mg. In addition, a non-steroidal anti-inflammatory drug (NSAID) will be given according to in-house protocol unless contraindications exist. We also recommend that Dexamethasone is given intravenously (8 mg) at the time of blockade.

## 9.3 Intervention

Subjects who are randomized to intervention will receive a paravertebral block at the end of the thoracic phase of surgery. Local anesthetics injected under thoracoscopic vision in 1-4 sites in the intercostal space 3-8 according to local routines. As always, attention to not inject in vessels (aspiration) is crucial. Abdominal port sites are also injected according to local routines. Permitted drugs and combinations are:

- Monotherapy, preferably bupivacain 2,5mg/ml (total volume 40-60ml). Alternatively, ropivacain 3,75mg/ml (total volume 40-60ml) can be used.
- Dexamethasone or betamethasone iv 8 mg
- Klonidin 75-150 µg iv (optional per center but same in both arms)

In addition, patient-controlled analgesia with opioids according to local protocols is used in this arm.

### 9.3.1 Training and quality control

All participating centers have good knowledge of the control arm EDA. For the intervention, an instructional film is provided, and at least 5 cases of experience with this method is recommended before start of randomization.

Link to instruction film:

<https://www.dropbox.com/scl/fi/zlggsfpe7vzftn2p9t6u6/Paravertebral-single-shot-analgesia-BALANCE-trial.mp4?rlkey=3hyhx4euyj7x1vp25xgjkw9d&e=1&dl=0>

Trial ID:	ISRCTN16853684
Version No:	1.0
Date:	January 27 th 2026

## 9.4 Control

Subjects who are randomized to control will receive routine EDA according to local routines at level Th6-10. After correct placement of the epidural catheter, a local anesthetic (ropivacaine, levobupivacaine, or bupivacaine) is used and according to in-house protocols, an opioid will be added to the epidural solution.

## 9.5 Escape medication

Patients will be offered patient-controlled analgesia with opioids if EDA pain control is insufficient. Escape (intervention group) or re-insertion (control group) of EDA can also be offered and should be recorded in the eCRF. All opioids given will be recorded.

## 9.6 Investigational product

Not applicable.

## 9.7 Non-investigational product

Not applicable.

# 10 Methods for measurement of endpoints for clinical efficacy and safety

Baseline data will be collected in an electronic randomization module where clinical information and stratification variables will be entered by the site investigator no later than the day before surgery. An eCRF will be filled out for all outcomes at the first postoperative visit, 30 days postop. All study data will be transferred from the eCRF to the study database. Additional outcome data (survival) will be accrued at 3 and 5 years and added to the study database.

## 10.1 Methods for measurement

### 10.1.1 Primary endpoint

The primary endpoint of anastomotic leak will be assessed according to local routines. A CT with contrast swallow is performed on postoperative day 7. If this CT is not performed (prior CT performed on clinical suspicion or other reason), this is specified. When the eCRF is filled out, all anastomotic leaks up to 30 days will be recorded, including day of onset. The questions regarding the primary outcome will be:

- Anastomotic leak (yes/no)
- Anastomotic leak type (grade I-III according to Low et al.(14))
- Day of a diagnosed anastomotic leak (1-30/NA)

Trial ID:	ISRCTN16853684
Version No:	1.0
Date:	January 27 th 2026

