## 6.3 Primary endpoint

Anastomotic leak will be recorded at postoperative day 30 when completing the electronic Case Report Form (eCRF). Any subclinical leaks will also be recorded (mandatory CT peroral contrast day 7).

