## 7.2 Procedures and flowchart

Procedure	Screening Preoperative inclusion visit	Operation Baseline information and randomization	Postoperative day 1, 2, 3 and 7	Postop Day 30 (28-35)g	3 and 5 years postop
Incl/exclusion criteria	✓				
Informed consent	✓				
Medical history/concomitant medications	✓	✓			
Randomizationa	✓	✓			
Anastomotic leak			Day 7 b	✓ c	
Pain scored	✓		✓	✓	
Patient reported outcomee			✓	✓	
Weight	✓		✓	✓	
Registration of all secondary endpointsf				✓	
Registration of start of epidural and cumulative hours with vasopressor use				✓	
Survival data					✓

a Patients are randomized no later than 12h before surgery

b One CT scan to be performed on postoperative day 7

c All diagnosed anastomotic leaks will be recorded in the eCRF

d Measured using NRS

e Reported with QoR15

f Recorded secondary endpoints include: postoperative opioid use, overall complications according to Clavien-Dindo, rescue or reinsertion of EDA, pneumonia, hypotension, first day of unassisted movement, total operation time, total time in operating theater, days in hospital, and days in high-dependency unit

g Data completion of eCRF is ideally obtained at day 30, but a one-week variance is accepted (day of data completion is noted in the eCRF)

Trial ID:	ISRCTN16853684
Version No:	1.0
Date:	January 27 th 2026

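### The open-label trial leaves its primary leak yes/no to local routines, with no stated criterion for yes and no masked classifier

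*Protocol*

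**What the plan says.** On assessment, Protocol section 10.1.1 says: "The primary endpoint of anastomotic leak will be assessed according to local routines". It then schedules imaging: "A CT with contrast swallow is performed on postoperative day 7". The scan may be left out: "If this CT is not performed (prior CT performed on clinical suspicion or other reason), this is specified". The eCRF asks for leak as a yes/no item, the leak type as grade I-III by a cited consensus system, and the day of diagnosis.

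Section 6.3 adds: "Any subclinical leaks will also be recorded (mandatory CT peroral contrast day 7"). A flowchart footnote in section 7.2 reads: "All diagnosed anastomotic leaks will be recorded in the eCRF".

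On masking, section 9.1 says: "No blinding will be used during treatment". The only masked role it names is the statistician, at analysis after data lock. Under section 14.3 the investigator's eCRF entries are checked against source records. Section 12 gives the monitoring committee a safety review. No section provides for endpoint adjudication or masked CT reading.

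**The concern.** A primary endpoint that needs judgement should have a written criterion, and in an open-label trial the people applying it should where possible not know the arm. Here neither is stated. The consensus system applies to the grade, a question that arises only once a leak has been called. By contrast, pneumonia, a secondary endpoint, has a named definition in section 10.1.2.

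The protocol also has a direction in mind. Section 5 links epidural-related hypotension and its treatment to leak, reports more leaks under epidural in an earlier trial, and sets superiority as the aim. If staff who share that expectation judge borderline findings knowing the arm, their calls could drift towards it. Neither the check against source records nor the masking of statisticians would show this, because the call is already in the source. A CT-only leak is probably the most debatable case, and its status in the primary endpoint is not stated.

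**Working it through.** **1. The plan's own figure.** Inputs from section 13.1: 15% v 7.5%, power 80%, alpha 5%; two-sided from section 13.3. With unpooled variance,

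n = (1.960 + 0.842)² × (0.15×0.85 + 0.075×0.925) / 0.075² = 7.849 × 0.196875 / 0.005625 = 274.7, so 275 per group.

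The pooled-variance formula gives 278, and power at 275 per group is 79.6%. The stated 275 reproduces; this point disputes no figure in the plan.

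**2. False-positive rate if calls differ by arm.** The documents give no classification error rates, so the following are assumptions: true leak 12% in both arms (33 of 275 each), 275 analysed per arm, and an uncorrected two-sided chi-square test at 5%. The rejection probability is exact: the two binomial distributions are summed over all tables that the test rejects.

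| Recorded leak, epidural v paravertebral | Expected leaks | Probability of rejection |
|---|---|---|
| 12% v 12% (no shift) | 33 v 33 | 4.9% |
| 13% v 12% (one point, one arm) | 35.75 v 33 | 6.4% |
| 12% v 11% (one point, one arm) | 33 v 30.25 | 6.5% |
| 13% v 11% (one point each way) | 35.75 v 30.25 | 11.0% |
| 14% v 10% (two points each way) | 38.5 v 27.5 | 30.1% |

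Normal-approximation check for 13% v 11%: the pooled SE is √(2×0.12×0.88/275) = 0.02771 and the unpooled SE 0.02770. The upper tail is Φ((0.02 − 1.96×0.02771)/0.02770) = Φ(−1.239) = 0.108. The lower tail adds 0.004, giving 11.1%.

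In the last two rows nearly all rejections (10.6 of 11.0 and 30.1 of 30.1 percentage points) favour paravertebral block. That follows from the direction assumed for the shift.

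**3. How few calls matter.** At the planned rates about 41 v 21 leaks are expected in 275 per arm. Chi-square = 550 × (41×254 − 234×21)² / (275 × 275 × 62 × 488) = 7.27, p = 0.007. Moving three calls in each arm towards the other (38 v 24) gives chi-square 3.56, p = 0.059.

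**4. What the day-7 CT covers.** A scan at the same time in both arms limits one open-label bias, that of looking harder in one arm. It does not settle how an equivocal scan is read. It may be omitted after an earlier CT done on clinical suspicion, so an unmasked team can influence when imaging happens. Leaks diagnosed clinically or on other days also enter the primary endpoint, which runs to day 30.

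**The case against.** The strongest reply is that the protocol already standardises a good deal: the same contrast CT is scheduled in both arms, an omission has to be explained, a consensus grade is collected, and entries are verified against source. The reference to local routines may also concern the diagnostic work-up rather than the criterion for yes, since the sentences after it deal with imaging. Much of this stands. A reader might infer that each site uses its own definition of leak. The text does not show that; it shows only that no criterion for yes is printed.

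The figures above also rest on assumed shifts, and a one-point shift in a single arm moves the false-positive rate only from 4.9% to 6.4-6.5%. That is correct, and the lower case belongs beside the higher ones.

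The remedy is incomplete too. A radiologist may see the arm in the chart, and masking the day-7 request does nothing for leaks found outside that scan. A reader might therefore want to add an analysis restricted to leaks that led to treatment, using the grade. The protocol does not print what grades I-III mean, and if they reflect treatment, unmasked staff chose it. That analysis cannot be relied on to remove the bias.

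What the reply does not meet is the gap itself: no written criterion for yes, and nobody who classifies the endpoint stated to be masked. Who judges the endpoint, by what rule and with what knowledge has to be fixed before recruitment; an analysis plan cannot repair it later.

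**Conclusion.** The point holds as a weakness of design that can be reduced at small cost. The primary yes/no has no stated criterion, the status of CT-only leaks is open, and masking is stated only for the statisticians.

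Under the assumptions above (12% true leak, 275 per arm, unadjusted chi-square as a stand-in for the adjusted logistic model in section 13.3), the false-positive rate ranges from about 6.4% to 30%, depending on the assumed shift, against 4.9% with none.

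A reader might go further and conclude that the trial will inflate the benefit of paravertebral block. The documents do not support that: they establish neither the size nor the direction of any bias. Nor do they support calling the remedy free, since they give no costs and every site would have to change its CT requests.

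**What to change.** In section 10.1.1, replace the reference to local routines with one yes/no criterion for all sites. The definition in the consensus reference already cited for grading is a candidate, if that reference contains one; the protocol does not show whether it does. State there and in section 6.3 whether a subclinical, CT-only leak counts in the primary endpoint.

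Require that the day-7 CT request and the clinical summary sent with it do not give the analgesia arm, and that the day-7 leak call is taken from the resulting report.

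The cost is protocol wording and an instruction to sites, with no added scan or reader. The protocol should say plainly that the masking is partial: the reader may see the chart, and leaks diagnosed clinically, on other days, or when the day-7 CT is omitted are not covered. For those leaks the common criterion is the main safeguard. At version 1.0, with a planned start in Q3 2026, the change can be made before recruitment.

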### 10.1.2 Secondary endpoints

- Postoperative pain will be evaluated at baseline, and on day 1, 2, 3, 7, and 30 with NRS (0-10) Appendix 1.
- Total postoperative opioid use (enteral and parenteral) in milligrams.
- Patient-reported quality of postoperative recovery will be measured on day 1, 2, 3, 7, and 30 with QoR15(12), Appendix 2.
- Overall complications will be registered in the eCRF at day 30:
  - Complication according to Clavien-Dindo (1-5)
  - Definition of highest graded complication (free text)
- Procedure-specific complications, epidural or paravertebral analgesia including inadequate sensory block, rescue (intervention group)/re-insertion (control group) of EDA (Y/N)
- Pneumonia, according to Seesing et al. (15)
- Blood pressure measured continuously for the first 12 hours and at least three times per day for the following five days.
- Intervention for hypotension (vasoactive drugs/fluids).
- POD of unassisted ambulation > 10 meters
- Total operation time (time from first incision to last suture in minutes)
- Total time used in operating theater (minutes)
- Patient weight is assessed at baseline, and on POD 1, 2, 3 and 7
- Length of hospital stay (days)
- Length of stay in high-dependency unit (days)
- Overall survival will be reported by the investigators during the course of the study

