## 11 Handling of Adverse Events

All complications and other outcomes will be recorded in the eCRF as described above. No new treatments or drugs are investigated in this trial and thus no adverse event recording or evaluation outside the DSMC evaluations are planned.

Local Anesthetic Systemic Toxicity, LAST

LAST is a very rare condition in which systemic effects from local anesthetics (both epidural and other peripheral use) can cause CNS and cardiac toxicity. It is caused by supratherapeutic plasma concentrations, often caused by an inadvertent intravascular injection. This occurs in less than 1/1000 patients and a recent study observed no cases of LAST in over 9000 peripheral nerve blocks. With the doses used in clinical practice and correct injection technique under direct thoracoscopic vision, risks are very low and treatment, including lipid emulsion injection, is known in all participating centers.

Trial ID:	ISRCTN16853684
Version No:	1.0
Date:	January 27 th 2026

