## 12 Independent Data Monitoring and Safety Committee

The Data Monitoring and Safety Committee (DMSC) will be presented with a complete list of complications and other outcomes from each of the two trial arms after 100 and 250 patients have been included in the trial. The DMSC will then at these points in time make an evaluation of patient safety in the trial. The DMSC will, after their assessment, present a brief report to the trial steering committee and, if serious safety issues are detected, actions will be taken to address these. Ultimately, if such serious safety issues cannot be addressed in any other effective way, the trial may be stopped.

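### Apart from complications with their own items, section 10.1.2 describes only each patient's highest-graded complication, which does not support the complete list promised in sections 11 and 12

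*Protocol*

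**What the plan says.** Two sections of the protocol promise full recording. Section 11 (Handling of Adverse Events) states: "All complications and other outcomes will be recorded in the eCRF as described above". Section 12 says that after 100 and 250 included patients the committee "will be presented with a complete list of complications and other outcomes from each of the two trial arms", and that unresolved serious safety issues may lead to the trial being stopped.

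The description that section 11 points back to is in section 10.1. For overall complications, section 10.1.2 lists two items at day 30: "Complication according to Clavien-Dindo (1-5") and "Definition of highest graded complication (free text").

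Other items record particular events whatever their rank. Section 10.1.1 says of the primary endpoint that "all anastomotic leaks up to 30 days will be recorded, including day of onset", with a grade. Section 10.1.2 adds "Procedure-specific complications, epidural or paravertebral analgesia including inadequate sensory block", epidural rescue or re-insertion, pneumonia and intervention for hypotension. Section 10.1.3 adds vasopressor dose and hours.

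On any further source of safety data, section 11 says that "no adverse event recording or evaluation outside the DSMC evaluations are planned".

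**The concern.** The committee's review and the descriptive safety reporting in section 13.3 can only show what the eCRF holds. If a patient has several complications and the form asks for the type of the worst one only, the lesser ones drop out of the listing unless they have an item of their own. The events at risk are those unrelated to the block or epidural and without a separate item, for example a cardiac event, a respiratory event other than pneumonia, or surgical bleeding.

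The loss need not be equal between arms. A leak can be the event that takes the single text slot, and the trial is planned on the expectation that leaks are twice as frequent under epidural analgesia. If that is true, lesser events would be hidden more often in the control arm, and the by-arm listings of other complications would not be strictly comparable. A statistical analysis plan cannot repair this, because it cannot recover events that were never entered.

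**Working it through.** **1. The passages side by side**

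| Place in the protocol | Content |
|---|---|
| Section 11 | All complications are in the eCRF, as described earlier |
| Section 12 | The committee receives a complete list by arm |
| Section 10.1.2, overall complications | Clavien-Dindo grade; type of the highest-graded complication only |
| Sections 10.1.1 to 10.1.3, own items | Leak, pneumonia, epidural or paravertebral complications, epidural rescue or re-insertion, treated hypotension, vasopressor use |
| Section 6.4 and section 7.2, footnote f | The same headings; no itemised list of other complications |
| Section 11, last part of its opening paragraph | No recording planned beyond the committee evaluations |

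Take a patient with a leak and a lower-graded cardiac event. The leak has its own item and, as the higher-graded event, also fills the free text. The cardiac event has no described field for its type. If the grade item is completed per patient, the cardiac event leaves no trace. If it is completed per event, a grade is left without a type. On neither reading does the list become complete.

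**2. How far leak could make the loss differ by arm**

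Inputs from section 13.1: leak 15% (control) and 7.5% (intervention), 275 per arm. That sample size reproduces with unpooled variance: (1.960 + 0.842)² × (0.15 × 0.85 + 0.075 × 0.925) / 0.075² = 274.7, so 275. The present point does not depend on it.

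Patients whose text slot could be taken by a leak, with equal arms assumed at the two committee looks:

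| Stage | Per arm | Control | Intervention |
|---|---|---|---|
| First look | 50 | 50 × 0.15 = 7.5 | 50 × 0.075 = 3.75 |
| Second look | 125 | 125 × 0.15 = 18.75 | 125 × 0.075 = 9.4 |
| Full trial | 275 | 275 × 0.15 = 41.25 | 275 × 0.075 = 20.6 |

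These are upper bounds on masking by leak. The leak must also be the highest-graded event, and the patient must also have another complication without its own item. The between-arm difference from this route is at most 15 − 7.5 = 7.5 percentage points of patients.

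**3. An illustration of the overall loss**

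The protocol gives no number of complications per patient, so this step rests on an outside assumption. Let the number of complications without their own item be Poisson with mean λ per patient, and let one be described in each affected patient. The share left undescribed is 1 − (1 − e^(−λ))/λ.

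| λ (assumed) | Share undescribed |
|---|---|
| 0.3 | 14% |
| 0.5 | 21% |
| 1.0 | 37% |
| 1.5 | 48% |

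The share is larger if a leak or pneumonia takes the slot. The range shows only that the loss depends strongly on an unknown quantity.

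**The case against.** The strongest reply is that the events closest to the trial question are all recorded separately. That is right. A reader might infer that the eCRF captures nothing but the worst complication, and sections 10.1.1 to 10.1.3 do not support that. Systemic local anaesthetic toxicity and paracostal bleeding, which the protocol names as risks, may also fit the item for epidural or paravertebral complications, although it mentions neither.

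Second, the eCRF form is not reproduced, and the Clavien-Dindo item does not say whether one grade is given per patient or per event. It is therefore too firm to say that lesser events will never be captured. But per-event grades would still lack a type, and asking for the definition of the highest-graded event alone points to a per-patient summary.

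Third, section 11 excludes recording only outside the committee evaluations, which could be read as leaving room for fuller reporting to the committee. No such data source is described anywhere, so this does not close the gap.

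Fourth, a reader might infer that the secondary objective on overall and procedure-specific complications is distorted. Section 6.4 makes that objective operational as Clavien-Dindo grade, epidural rescue or re-insertion, and pneumonia. Each has an item, and a patient's highest grade is not hidden by a lesser event. That inference fails.

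Finally, a reader might put a figure on the loss by assuming that 40% to 60% of patients have a complication and a third to a half of these have more than one: 0.40 × 0.33 = 13% to 0.60 × 0.50 = 30%. The rates are not in the protocol, and the product counts patients with more than one complication without removing those whose further events have their own items. It is not an estimate of loss.

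**Conclusion.** The point holds as a mismatch between what sections 11 and 12 promise and what section 10.1.2 describes. Followed as written, the eCRF cannot supply a complete list of complications by arm, because a lesser complication without its own item has no described field for its type when a worse event occurs in the same patient.

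What is affected is the committee's listing and the descriptive safety listing, not the primary endpoint or the highest-grade endpoint. The size of the loss cannot be derived from the protocol. A difference between arms is possible if leak rates differ as planned, bounded for the leak route by the 7.5 percentage points shown above. The conclusion rests on section 10.1 being the full description of what is collected, which is how section 11 uses it. It should be resolved before recruitment starts.

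**What to change.** Replace the single free-text item in section 10.1.2 with one eCRF row per complication up to day 30, holding type, Clavien-Dindo grade and day, and derive the highest grade per patient from these rows. The types can be taken from the esophagectomy complications consensus that section 10.1.1 already cites for leak grading. Sections 11 and 12 can then stand.

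If the extra rows are not wanted, restate sections 11 and 12 so that they promise only what the eCRF collects: the separately recorded events and the highest-graded complication. This makes the text consistent but leaves the committee with the smaller data set.

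The first option costs a few form fields and slightly more data entry at the day-30 visit. The protocol is version 1.0 with a planned start in Q3 2026, so the change is cheap now; later it would need retrospective chart review. The second option costs only a wording change. Neither alters clinical management.
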